#### **4. Statistical Analysis:**

For each subject, we will record the presence and location of abnormal uptake. For the PET/CT images, we will generate a region-of-interest (ROI) around each area of morphologic abnormality to calculate a mean standardized uptake value (SUV), a maximum SUV, and a target-to-background ratio. A target-to-background ratio of at least 2.0 will be used to score a particular ROI as positive. These values will be compared quantitatively with those of contralateral normal joint. Radiotracer uptake pattern on each modality will be classified according to known methods (29). Then, we will descriptively and quantitatively correlate Ga-citrate PET/CT findings with those of F-FDG PET/CT. Using the macroscopic intraoperative and later tissue histology and culture as the gold standard, sensitivity, specificity, and positive and negative predictive values of Ga and FDG PET will be calculated and compared with each other. We will also review the PET/CT images for multifocal involvement, if any.

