#### **Statistical Analysis:**

Primarily, all variables will be analyzed and overall, descriptively, as follows:

- Mean, standard deviation, median and range for continuous variables
- Median, range and frequency distribution for discrete (ordinal) variations

- The results of the imaging modalities (PET, CT and MRI) will be classified as true positive (TP), true negative (TN), false positive (FP), or false negative (FN) according to the reference standard.
- The McNemar test of correlated properties will be used to statistically compare the imaging results of Ga-citrate and F-FDG PET with MRI and diagnostic CT.
- The student t-test will be used to statistically compare the quantitative findings of Ga-citrate and F-FDG scans.
- Analysis will be done on a lesion basis and on a patient basis.
- All P values, <0.05 will be considered significant.
- Cohen's k-statistic with 95% confidence intervals will be calculated to show the degree of association between the techniques.

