For each subject, we will record the presence and location of abnormal uptake. For the PET/CT images, we will generate a region-of-interest (ROI) around each area of morphologic abnormality to calculate a mean standardized uptake value (SUV), a maximum SUV, and a target-to-background ratio. A target-to-background ratio of at least 2.0 will be used to score a particular ROI as positive. These values will be compared quantitatively with those of contralateral normal joint. Radiotracer uptake pattern on each modality will be classified according to known methods. Then, we will descriptively and quantitatively correlate Ga-citrate PET/CT findings with those of F-FDG PET/CT. Using the macroscopic intraoperative and later tissue histology and culture as the gold standard, sensitivity, specificity, and positive and negative predictive values of Ga and FDG PET will be calculated and compared with each other. We will also review the PET/CT images for multifocal involvement, if any.

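### Tests are planned per lesion and per patient with no primary unit, no stated pairing, no allowance for several ROIs in one patient, and no rule for the patient-level result

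*Protocol*

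**What the plan says.** The bullet list closing section 4 of the protocol and the bullet list in the SAP are the same on this point. They open with "Primarily, all variables will be analyzed and overall, descriptively, as follows". They then say "The McNemar test of correlated properties will be used to statistically compare the imaging results of" the two PET scans with MRI and diagnostic CT, and "The student t-test will be used to statistically compare the quantitative findings of" the gallium and FDG scans. Cohen's kappa is to have 95% confidence intervals. Two general statements cover the whole list: "Analysis will be done on a lesion basis and on a patient basis" and "All P values, <0.05 will be considered significant".

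The text before the bullets defines the lesion unit. The reader will "generate a region-of-interest (ROI) around each area of morphologic abnormality", and "A target-to-background ratio of at least 2.0 will be used to score a particular ROI as positive". The protocol adds: "We will also review the PET/CT images for multifocal involvement, if any". Uptake pattern on each modality is also to be classified by known methods; the protocol gives a reference for these and the SAP does not. Sensitivity, specificity and predictive values are calculated against operative findings, histology and culture.

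Neither document names a primary unit, states that the t-test is paired, gives a method for correlated ROIs, or says what turns ROI scores or uptake patterns into one result per patient.

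**The concern.** Followed as written, the lesion-basis tests treat every ROI as an independent observation, although ROIs from one patient may resemble each other. If the differences between techniques are correlated within patients, the standard errors are too small and the 0.05 threshold does not hold.

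Two further gaps do not depend on clustering. Both tracers are imaged in the same patients, so a t-test that ignores pairing uses the wrong standard error even with one ROI per patient. And with two units tested at 0.05 and neither primary, the plan does not say which result counts if they disagree. The patient-basis accuracy figures, which are the purpose of the study, also depend on a combining rule that is left open until after the images are read.

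**Working it through.** **Inputs from the documents.** 17 patients (protocol, Sample Size, given without a derivation, so there is no planned power to reproduce); threshold 0.05 (taken as two-sided); ROI positivity at a target-to-background ratio of at least 2.0.

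**Assumed, because the documents give no values.** ROIs per patient: one each; sparse (14 patients with one, three with two); two each; three each. ROI-value ICC 0.5 within each technique. For McNemar, 60% of ROIs positive on both techniques. All error rates below are simulated with no true difference.

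**Step 1: baseline.** With one ROI each, the paired t-test gives 5.0%, as it should.

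**Step 2: pairing, one ROI each.** With cross-tracer correlation r, the true variance of the mean difference is 2σ²(1−r)/17, but an unpaired test uses 2σ²/17. Its standard error is too large by 1/√(1−r): 1/√0.7 = 1.20 at r = 0.3 and 1/√0.5 = 1.41 at r = 0.5. Simulated type I error is 2.1% and 0.8%. The test is conservative and loses power.

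**Step 3: which correlation matters.** Split the variance of an ROI value into a patient effect shared by both techniques (s), a technique-specific patient effect (τ) and a remainder (1−s−τ), with s + τ = 0.5. In the within-ROI difference the shared effect cancels, so the ICC of the differences is ρ = τ/(1−s):

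- fully shared (s = 0.5, τ = 0): ρ = 0
- partly shared (s = 0.3, τ = 0.2): ρ = 0.2/0.7 = 0.286
- nothing shared (s = 0, τ = 0.5): ρ = 0.5

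**Step 4: lesion-level paired t-test.** With m ROIs per patient, the design effect is DE = 1 + ρ(Σm²/Σm − 1), and type I error is about 2[1 − Φ(1.96/√DE)]. Σm²/Σm is (14 + 12)/20 = 1.3 in the sparse case, 2 with two each and 3 with three each. When nothing is shared, DE is 1.15, 1.5 and 2.0, which gives about 6.8%, 11.0% and 16.6%. Simulation agrees:

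| Patient effect | Sparse | Two each | Three each |
|---|---|---|---|
| Fully shared | 4.9% | 4.8% | 5.0% |
| Partly shared | 5.9% | 8.4% | 11.9% |
| Nothing shared | 6.7% | 11.2% | 17.1% |

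**Step 5: lesion-level McNemar (chi-square form).** Fully shared: 4.7%, 4.3% and 4.9%. Nothing shared: about 5%, 9% and 14%.

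**Step 6: kappa.** The effect is mild. At ICC 0.5, nominal 95% intervals that ignore clustering cover about 92% with repeated ROIs. With one ROI each they cover about 89%, from small numbers alone.

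**Step 7: combining rule.** Take an uninfected patient with two ROIs and an assumed per-ROI specificity of 80%. If any positive ROI makes the patient positive, patient-level specificity with independent ROIs is 0.8² = 64%. If both must be positive, it is 1 − 0.2² = 96%. At a latent correlation of 0.8 the figures are 73% and 87%.

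**Step 8: check of the fix.** A paired t-test on patient means held 4.8–5.2% in every setting. A cluster-adjusted McNemar with a t reference on 16 df held 4.6–5.6%. An unpaired t-test on patient means stays at about 2.1% and 0.8% for r = 0.3 and 0.5, so averaging within patients does not remove the need to state pairing.

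**The case against.** The strongest reply is that the problem may be small. The exclusion criteria rule out active inflammation or infection away from the prosthetic joint, so many remote ROIs are unlikely. With one ROI per patient the clustering issue disappears, and in the sparse case it is slight. The protocol calls the study preliminary and a pilot, the analysis is descriptive first, and a patient-basis analysis is already planned. All of this stands and limits the severity. It does not rule out several ROIs around one prosthesis, and it does not settle pairing, the primary unit or the patient-level rule.

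A reader might infer that positive correlation between a patient's ROIs is enough to make the lesion-level tests too liberal. It is not: step 3 shows that a patient effect common to both techniques cancels, and the table shows no inflation then even with three ROIs each.

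A reader might also infer that the plan offers nothing from which a patient result could come. The cited pattern classification may supply a joint-level reading, and recording the presence of abnormal uptake for each subject could be read as an any-uptake rule. But neither document says that either one sets the patient result, or how it relates to the ratio of 2.0.

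**Conclusion.** The gaps are plain in both documents: no allowance for clustering, no statement of pairing, no primary unit and no stated route to the patient result. The pairing error needs only a positive cross-tracer correlation and applies even with one ROI each (about 2.1% and 0.8% at assumed r of 0.3 and 0.5).

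The clustering error is conditional. It ranges from none to about 17% for the paired t-test and 14% for chi-square McNemar. The top of each range needs three ROIs in every patient and no shared patient effect. The documents do not support a claim that lesion-level P values will be badly inflated, because they give neither ROI counts nor correlations. Nor does clustering by itself bias sensitivity or specificity. Severity is low to moderate: the plan needs this clarified, and the pilot is not invalidated.

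**What to change.** In the bullets of protocol section 4 and of the SAP:

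1. Name the per-patient analysis of the index joint as the primary inferential one, with one result per technique: gallium PET, FDG PET, MRI and diagnostic CT. MRI and CT must be included because McNemar is written as comparing PET with them. Set one combining rule before images are read, and say whether the cited pattern classification or the ROI ratio of at least 2.0 determines the result.
2. State that the gallium–FDG t-test is paired and is done on patient means.
3. Report lesion-level results descriptively, or with the patient as cluster: for example, a cluster-adjusted McNemar with a t reference on 16 df, and kappa intervals from resampling patients.

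The change is wording only, with no extra patients or scans. The price is wider intervals than the naive paired lesion-level ones when differences are correlated within patients. At an ICC of the differences of 0.5, they are about 1.08 times as wide in the sparse case, 1.28 times with two ROIs each and 1.50 times with three each.

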## 5. **Reporting Results**

The study was previously supported by the research grant from New Jersey Health Foundation (NJHF). As per the requirement of the NJHF an interim report on the progress of the project and a final narrative report have to be submitted to NJHF. In addition, NJHF Vice President of Communications should be consulted before any communications activities, including but not limited to such media as organization publications, trade publications, newspapers, magazines, radio and television.

## **Statistical Analysis Plan:**

**Title of Study:** Novel Gallium 68 Citrate Imaging in Orthopedic Infections.

**Principal Investigator:** [name]

**NCT ID:** 20160000134

**Date:** 02/06/2018

The purpose of the study is to demonstrate the feasibility and evaluate the accuracy of 68Gallium (Ga)-citrate positron emission tomography/computed tomography (PET/CT) in diagnosing prosthetic joint infection and compare it with fluorine-fluorodeoxyglucose-positron emission tomography/computed tomography (FDG-PET/CT). We expect that Ga-citrate PET/CT will serve as a novel molecular-based sensitive functional imaging modality superior to FDG-PET/CT. We intend to translate the results of this preliminary study to fuel larger studies in the utility of Ga-citrate PET/CT to evaluate prosthesis complications, where current available imaging techniques are challenging.

For each subject, we will record the presence and location of abnormal uptake on both 67Gallium Citrate and Fluorodeoxyglucose PET/CT scans. We will then generate a region-of-interest around each area of morphologic abnormality to calculate a mean standardized uptake value (SUV), a maximum SUV, and a target-to-background ratio. These values will be compared with those of contralateral normal joint. Radiotracer uptake pattern on each modality will be classified according to known methods. Using the macroscopic intraoperative and later tissue histology and culture as the gold standard, sensitivity, specificity, and positive and negative predictive values of Ga and FDG PET will be calculated and compared with each other.

For each subject, we will record the presence and location of abnormal uptake. For the PET/CT images, we will generate a region-of-interest (ROI) around each area of morphologic abnormality to calculate a mean standardized uptake value (SUV), a maximum SUV, and a target-to-background ratio. A target-to-background ratio of at least 2.0 will be used to score a particular ROI as positive. These values will be compared quantitatively with those of contralateral normal joint. Radiotracer uptake pattern on each modality will be classified according to known methods. Then, we will descriptively and quantitatively correlate Ga-citrate PET/CT findings with those of F-FDG PET/CT. Using the macroscopic intraoperative and later tissue histology and culture as the gold standard, sensitivity, specificity, and positive and negative predictive values of Ga and FDG PET will be calculated and compared with each other. We will also review the PET/CT images for multifocal involvement, if any.

## Statistical Analysis:

- Primarily, all variables will be analyzed and overall, descriptively, as follows:
- Mean, standard deviation, median and range for continuous variables
- Median, range and frequency distribution for discrete (ordinal) variations

- The results of the imaging modalities (PET, CT and MRI) will be classified as true positive (TP), true negative (TN), false positive (FP), or false negative (FN) according to the reference standard.
- The McNemar test of correlated properties will be used to statistically compare the imaging results of Ga-citrate and F-FDG PET with MRI and diagnostic CT.
- The student t-test will be used to statistically compare the quantitative findings of Ga-citrate and F-FDG scans.
- Analysis will be done on a lesion basis and on a patient basis.
- All P values, <0.05 will be considered significant.
- Cohen's k-statistic with 95% confidence intervals will be calculated to show the degree of association between the techniques.
